6.2.6. Change From Baseline in SALT Score

- Change from baseline in SALT scores at Weeks 4, 8, 12, 18, 24, 28, 34, 40, and 48.
- Population: FAS.
- Statistical Method: MMRM up to Week 24. MMRM for initial active treatment groups for entire duration. Descriptive statistics for all treatment groups over the entire duration.
- Missing Data: Handled in MMRM model. Observed Cases will be used for the descriptive analysis.

6.2.7. Eyebrow Assessment Score

- Response based on at least a 2-grade improvement or a normal EBA score at Weeks 4, 8, 12, 18, 24, 28, 34, 40, and 48.
- Population: FAS on the subset of subjects who do not have normal (score of 3 on the EBA) eyebrow at baseline.
- Statistical Method: MN up to week 24. Descriptive method for entire duration.
- Missing Data: Exclude missing due to COVID-19, consider missing due to other as non-responders.

6.2.8. Eyelash Assessment Score

- Response based on at least a 2-grade improvement or a normal ELA score at Weeks 4, 8, 12, 18, 24, 28, 34, 40, and 48.
- Population: FAS on the subset of subjects who do not have normal (score of 3 on the ELA) eyelash at baseline.
- Statistical Method: MN up to week 24. Descriptive method for entire duration.
- Missing Data: Exclude missing due to COVID-19, consider missing due to other as non-responders.

6.2.9. PGI-C Response

The analysis of PGI-C as a key secondary endpoint for the EMA and competent authorities in the VHP countries was described in [Section 6.1.3](#). This section describes the analysis of the PGI-C response at all timepoints as a secondary endpoint for the overall study and for the FDA/PMDA.

- PGI-C response defined as PGI-C score of “moderately improved” or “greatly improved” at Weeks 4, 8, 12, 18, 24, 34, 40, and 48.
- Population: FAS.
- Statistical Methods: MN up to week 24. A descriptive summary of the distribution of subjects according to each category of PGI-C will be provided.
- Missing Data: Exclude missing due to COVID-19, consider missing due to other as non-responders.

6.2.10. Alopecia Areata Patient Priority Outcomes (AAPPO) Scale

AAPPO was measured at baseline, Weeks 4, 8, 12, 18, 24, 34, 40, and 48. Endpoints include:

- Current hair loss on scalp, eyebrows, eyelash, and body hair (Items 1-4) for each individual item scored as 0='no hair loss', 1='little hair loss' and 2-4='moderate-complete hair loss'.
- Improvement on AAPPO items 1-4 among participants with a baseline score 2-4 indicating moderate-complete hair loss who achieved a score of 0='no hair loss' or 1='little hair loss'.
- Change from baseline in AAPPO Emotional Symptoms domain score, where Emotional Symptoms domain score is defined as mean of items 5-8.
- Change from baseline in AAPPO Activity Limitations subscore, where Activity Limitations subscore is defined as mean of items 9-11.
- Population: FAS.
- Statistical Methods:
 - MN for Proportion of patients with Improvement on Items 1-4. A descriptive summary of the distribution of subjects according to each category of AAPPO Items 1-4 will be provided.
 - MMRM for change from baseline in AAPPO Emotional Symptoms and Activity Limitations up to week 24. MMRM for initial active treatment groups for entire duration. Descriptive statistics for all treatment groups over the entire duration.
 - Missing Data: Exclude missing due to COVID-19, consider missing due to other as non-responders. For change from baseline, missing values are handled in the MMRM model. Observed Cases will be used for the descriptive analysis.

6.3. Exploratory Endpoints

Exploratory binary endpoints will be summarized using descriptive statistics unless specified otherwise.

6.3.1. 50% Improvement in SALT Score (SALT50)

- Response based on a 50% improvement in SALT score from baseline (SALT50) at Weeks 4, 8, 12, 18, 24, 28, 34, 40, and 48.
- Population: FAS.
- Statistical Method: Descriptive statistics.
- Missing Data: Observed Case.

6.3.2. Absolute SALT Score

- Absolute SALT scores at Baseline, Weeks 4, 8, 12, 18, 24, 28, 34, 40, and 48.

- Population: FAS.
- Statistical Method: Descriptive statistics.
- Missing Data: Observed Case.

6.3.3. Improvement on PGI-C

- Improvement on PGI-C defined as “slightly improved”, “moderately improved”, or “greatly improved” at Weeks 4, 8, 12, 18, 24, 34, 40, and 48.
- Population: FAS.
- Statistical Method: Descriptive statistics.
- Missing Data: Observed Case.

6.3.4. Improvement on P-Sat

- Improvement on each item of the P-Sat (ie, amount of hair, quality of new hair, and overall) defined as slightly, moderately, or very satisfied for each item at Weeks 4, 8, 12, 18, 24, 34, 40, and 48.
- Population: FAS.
- Statistical Method: Descriptive statistics.
- Missing Data: Observed Case.

6.3.5. Change From Baseline in the EQ-5D-5L/EQ-5D-Y

- Change from baseline in EuroQoL 5 Dimensions (EQ-5D-5L) in adults or EuroQoL 5 Dimensions-Youth (EQ-5D-Y) in adolescents at Weeks 4, 12, 24, and 48.
- Population: FAS.
- Statistical Method: Descriptive statistics for EQ-5D VAS score and Index Value for adults and adolescents separately. Counts and percent of patients in each category of for each of the 5 Dimensions, separately for adults and adolescents.
- Missing Data: Observed Case.

6.3.6. Change From Baseline in the AARU Questions

- Proportion of subjects with any HCP visits at Weeks 12, 24, 34, and 48.
- Among those with HCP visits, mean total number of visits for any reason, mean change from baseline in total number of visits for any reason, mean total number of visits related to AA and mean change from baseline in AA-related visits at Weeks 12, 24, 34, and 48.

- Population: FAS.
- Statistical Method: Descriptive Statistics.
- Missing Data: Observed Case.

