#### **7.8.8. Alopecia Areata Resource Utilization (AARU)**

The Alopecia Areata Resource Utilization (AARU) is a PRO that measures the resource utilization associated with AA. The AARU is a 3-item questionnaire which asks patients about medical or nonmedical practitioner visits, cosmetic covering of hair loss, and career impact they may have had over the past 3 months.

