#### **9.2.4. Analysis of Other Endpoints**

Analysis of other endpoints will be conducted using descriptive statistics.

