3.2. Other Endpoints

3.2.1. Exploratory Endpoints

- Collection of banked biospecimens unless prohibited by local regulations or ethics committee decision. Additional information on collection and potential use is provided in the Banked Biospecimens section in the protocol.
- Response based on a 50% improvement in SALT score from baseline (SALT50) at Weeks 4, 8, 12, 18, 24, 28, 34, 40, and 48.

- Absolute SALT scores at Baseline, Weeks 4, 8, 12, 18, 24, 28, 34, 40, and 48.
- Improvement on PGI-C defined as “slightly improved”, “moderately improved”, or “greatly improved” at Weeks 4, 8, 12, 18, 24, 34, 40, and 48.
- Improvement on Patient Satisfaction with Hair Growth (P-Sat) items defined as slightly, moderately, or very satisfied at Weeks 4, 8, 12, 18, 24, 34, 40, and 48.
 - Will be analyzed for each individual item.
- Change from baseline in EuroQoL 5 Dimensions (EQ-5D-5L) in adults or EuroQoL 5 Dimensions-Youth (EQ-5D-Y) in adolescents at Weeks 4, 12, 24, and 48.
 - Will be analyzed for adults and adolescents separately. US specific utility weights¹ will be applied for the scoring of these endpoints;
- Change from baseline in Alopecia Areata Resource Utilization (AARU) at Weeks 12, 24, 34, and 48.
 - Proportion of subjects with any healthcare professional (HCP) visits.
 - Among those with HCP visits, mean total number of visits for any reason, mean change from baseline in total number of visits for any reason, mean total number of visits related to AA and mean change from baseline in AA-related visits.
- Change from baseline in Work Productivity and Activity Impairment: Alopecia Areata (WPAI:AA) at Weeks 12, 24, 34, and 48.
 - Change from baseline in absenteeism, presenteeism, work productivity loss (overall) and activity impairment in adults.
- Change from baseline in the depression subscale score of the Hospital Anxiety and Depression Scale (HADS) at Weeks 4, 8, 12, 24, and 48.
 - For the EMA and competent authorities in the VHP countries this endpoint will be analyzed as a secondary endpoint.
- Change from baseline in the anxiety subscale score of the Hospital Anxiety and Depression Scale (HADS) at Weeks 4, 8, 12, 24, and 48.
 - For the EMA and competent authorities in the VHP countries this endpoint will be analyzed as a secondary endpoint.
- Improvement on HADS among subjects with a baseline subscale score indicative of depression who achieved a “normal” subscale score indicative of an absence of depression at Weeks 4, 8, 12, 24, and 48.

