9.2. Details on Selected PRO Endpoints

AAPPO

The AAPPO is a 11-item scale. Items 1-4 are an assessment of current hair loss, eyebrow loss, eyelash loss and body hair loss and will be as such analyzed separately on a scale of 0-4, with 0 =‘no hair loss’ and 4=‘complete hair loss’. Items 5-8 are an assessment of emotional symptoms. Response choices on these items are scored from 0 =‘never’ to 4=‘always’. Items 9-11 are an assessment of activity limitations. Response choices on these items are scored from 0=‘not at all’ to 4= ‘completely’.

- AAPPO Items 1 through 4 are scored separately as 0=‘no hair loss’, 1=‘little hair loss’ and 2-4=‘moderate-complete hair loss’.
- Improvement on AAPPO items (1-4) among participants with a baseline score 2-4, indicating moderate-complete hair loss who achieved a score of 0=‘no hair loss’ or 1=‘little hair loss’.
- Emotional Symptoms: Mean of Items 5, 6, 7, 8 (missing rule: requires at least 2 non-missing responses; otherwise missing).
- Activity Limitations: Mean of Items 9, 10, 11 (missing rule: requires at least 2 non-missing responses; otherwise missing).

AARU:

- Assessment of total in-person and remote healthcare visits.
- Assessment of AA-related in-person and remote healthcare visits.
- Assessment of utilization of hair prostheses or camouflaging agents.
- Assessment of # of days hair prostheses or camouflaging agents were utilized.
- Percentage of patients not currently employed.
- Percentage of patients who have not sought employment due to alopecia areata.
- Number of opportunities for employment not sought due to alopecia areata.

WPAI –AA:

WPAI-AA is an adaptation of the WPAI:SHP (Specific Health Problem) version. Outcomes from this scale are expressed as impairment percentages, with higher numbers indicating greater impairment and less productivity. The questionnaire is scored as follows:

Questions:

- 1 = currently employed.

- 2 = hours missed due to specified problem.
- 3 = hours missed other reasons.
- 4 = hours actually worked.
- 5 = degree problem affected productivity while working.
- 6 = degree problem affected regular activities.

Scoring.

- Multiply scores by 100 to express in percentages.
- Percent work time missed due to problem (Absenteeism): $Q2/(Q2+Q4)$.
- Percent impairment while working due to problem (Presenteeism): $Q5/10$.
- Percent overall work impairment due to problem (Overall Work Impairment): $Q2/(Q2+Q4)+[(1-(Q2/(Q2+Q4)))x(Q5/10)]$.

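### Mean healthcare visits and their change are summarised only in subjects with visits, so observed zeros drop out on the natural reading and the mean change can be distorted either way

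*SAP*

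**What the plan says.** The AARU is an exploratory endpoint, collected at Day 1 and at Weeks 12, 24, 34 and 48. Protocol 7.8.8 describes three items, covering practitioner visits, cosmetic covering and "career impact they may have had over the past 3 months". The protocol's endpoint is simply change from baseline in AARU; it contains no subset restriction.

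The SAP turns this into two kinds of summary. SAP 6.3.6 first lists "Proportion of subjects with any HCP visits at Weeks 12, 24, 34, and 48". The next bullet then gives the visit counts, but restricted: "Among those with HCP visits, mean total number of visits for any reason, mean change from baseline in total number of visits", continuing with "mean total number of visits related to AA and mean change from baseline in AA-related visits at Weeks 12, 24, 34, and 48". SAP 3.2.1 uses the same restriction in the endpoint definition: "Among those with HCP visits, mean total number of visits for any reason".

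The population line in 6.3.6 is the FAS without qualification, the method is descriptive, and the missing-data line reads "Missing Data: Observed Case". The scoring appendix, SAP 9.2, lists "Assessment of total in-person and remote healthcare visits" and the AA-related equivalent with no restriction, but it specifies no analysis. Protocol 9.2.4 says "Analysis of other endpoints will be conducted using descriptive statistics".

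**The concern.** Neither SAP section says whether the subset is defined by visits at baseline, at the week summarised, or at either. Two features of the text point to the week summarised.

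- The restricted bullet directly follows one on the proportion with any visits at Weeks 12 to 48, and baseline is not among those time points.
- Where this SAP intends a baseline subset, it says so: eyebrow and eyelash scores (6.2.7, 6.2.8), AAPPO items 1-4 (6.2.10), HADS improvement (6.3.10, 6.3.11), CGI-AA improvement (6.3.13) and affected fingernails (6.3.14).

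On that reading, a change score is conditioned on its own follow-up value. The subjects with the most complete reduction, from some visits to none, leave the calculation. If treatment alters the chance of having any visit, the remaining subjects in each arm are no longer comparable, so the mean change is not a randomised comparison even at Weeks 12 and 24, before placebo subjects move to active treatment. At stake is a descriptive figure on resource use that serves the payer-relevant exploratory objective.

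**Working it through.** The documents give no visit rate, standard deviation or expected effect for the AARU, so there is no planned figure to reproduce. Every visit count below is an assumption chosen to show what the denominator does.

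**Step 1: arithmetic example (assumed).** Everyone has 2 visits at baseline. At Week 24, 50% on active and 20% on placebo have none; the rest still have 2.

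- Mean change, all subjects: active 0.5 × (-2) = -1.0; placebo 0.2 × (-2) = -0.4; difference -0.6.
- Mean change among those with visits at Week 24: 2 - 2 = 0 in both arms; difference 0.
- Proportion with any visit: active 50%, placebo 80%.

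**Step 2: simulation (assumed).** There were 1,000,000 subjects per arm, with Poisson visit counts and a gamma frailty of shape 1. Visit rates on placebo did not change. Two active-arm patterns were compared: a fraction of subjects stop visits entirely, or every subject's rate falls by 40%. Entries are active minus placebo in mean change, at a baseline mean of 2 visits.

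| Subjects included | 40% of active stop | All active rates fall 40% |
|---|---|---|
| All, zeros kept | -0.80 | -0.80 |
| Visits at the week summarised | 0.00 | -1.04 |
| Visits at baseline | -1.07 | -1.07 |
| Visits at either time | -1.07 | -1.05 |
| Proportion with any visit, placebo / active | 0.67 / 0.40 | 0.67 / 0.55 |

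**Step 3: range over baseline means of 0.5 to 4 visits.**

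- 20% of active stop: all subjects -0.10 to -0.80; week-specific subset 0.00 throughout.
- 40% of active stop: all subjects -0.20 to -1.60; week-specific subset 0.00 throughout.
- All active rates fall 40%: all subjects -0.20 to -1.60; week-specific subset -0.25 to -1.98.

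**Step 4: the unchanged placebo arm.** Selecting on a positive follow-up count makes mean change positive when nothing has changed. Under this model with baseline mean m, the expected follow-up count given at least one visit is 1 + m. The expected baseline count in the same subjects is (1 + m) - 1/(1 + m). The apparent rise is therefore 1/(1 + m): 0.67, 0.50, 0.33 and 0.20 for m = 0.5, 1, 2 and 4, matching the simulation.

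**Step 5: can the other planned output repair it?** Proportion with any visit × conditional mean count gives the all-subject mean count. In the Step 1 example that is 0.5 × 2 = 1.0 against 0.8 × 2 = 1.6, a difference of -0.6, which is correct. Mean change also needs the all-subject baseline mean, and neither 3.2.1 nor 6.3.6 lists it.

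**The case against.** The strongest reply is that the SAP has left a subset undefined rather than chosen a wrong one. If visits at baseline were meant, subjects who fall to zero stay in and the reduction shows (-1.07 in the table). This stands as far as it goes: the week-specific reading is an inference from the text. The readings nevertheless give different answers from the same data, so the wording cannot be left as it is. The either-time reading also still uses follow-up data to select subjects.

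Second, the two bullets can be read as a two-part summary, in which the proportion shows who has any visits and the conditional mean shows how many. This also stands for the mean count, as Step 5 shows. It does not rescue the mean change, which is listed separately and is the quantity affected.

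Third, the AA-related measure is only partly exposed if the subset means any HCP visit. A subject whose AA visits fall to zero but who sees another provider stays in and contributes the full reduction. That is correct, but it means a fall to zero AA visits is kept or dropped according to unrelated care.

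Fourth, SAP 9.2 lists visits without the restriction. That is a list of items, not an analysis, and does not override 6.3.6.

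A reader might go further and infer that the treatment benefit is hidden. The documents do not support that: the proportion with any visit is planned at the same weeks and is 50% against 80% in the very example where the mean change shows nothing.

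**Conclusion.** The point holds as a minor one. On the natural, week-specific reading, SAP 6.3.6 and 3.2.1 drop observed zeros and condition the mean change on a post-randomisation outcome. Depending on the pattern, the between-arm difference can vanish (-0.80 becomes 0.00) or be exaggerated (-0.80 becomes -1.04), and an unchanged arm can appear to rise by 0.20 to 0.67 visits. These sizes rest entirely on assumed visit rates; the documents allow no estimate for this trial.

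Two stronger conclusions are tempting and should not be drawn. One is that the comparison is biased toward no difference: the uniform-reduction case goes the other way, and nothing in the documents says which pattern to expect. The other is that the payer-relevant objective is defeated: that objective is also served by the proportion with any visit and by several other instruments, including WPAI:AA and EQ-5D. The AARU is summarised descriptively with no alpha allocated, so no hypothesis test, primary result or key secondary result is touched.

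**What to change.** In SAP 3.2.1 and 6.3.6, define the visit summaries, both any-reason and AA-related, as mean count and mean change from baseline in all FAS subjects with an observed AARU at baseline and at the week in question, counting no visits as 0. Present them beside the proportion with any visit. Keep the conditional mean number of visits only as additional description, and state the time point that defines its subset. Drop the conditional mean change.

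The cost is a wording change in two SAP sections and the matching table programs. It needs no new data. The protocol's AARU endpoint carries no restriction, and Protocol Section 9 calls for an amendment only for major changes to the primary endpoint definitions or their analyses, so none is required.

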6.3.7. Change From Baseline in the WPAI:AA Items

- Change from baseline in absenteeism (% work time missed due to AA), presenteesism (% impairment while working due to AA), work productivity loss (overall) due to AA and activity impairment due to AA at Weeks 12, 24, 34, and 48.
- Population: Adults in FAS.
- Statistical Method: Descriptive Statistics.
- Missing Data: Observed Case.

6.3.8. Change From Baseline in the Depression Subscale Score of HADS

- Change from baseline in the depression subscale score of the HADS at Weeks 4, 8, 12, 24, and 48.
- Population: FAS.
- Statistical Method: MMRM up to week 24. MMRM for initial active treatment groups for entire duration. Descriptive statistics for all treatment groups over the entire duration.
- Missing Data: handled in MMRM model. Observed Cases will be used for the descriptive analysis.

6.3.9. Change From Baseline in the Anxiety Subscale Score of HADS

- Change from baseline in the anxiety subscale score of the HADS at Weeks 4, 8, 12, 24, and 48.
- Population: FAS.
- Statistical Method: MMRM up to week 24. MMRM for initial active treatment groups for entire duration. Descriptive statistics for all treatment groups over the entire duration.
- Missing Data: handled in MMRM model. Observed Cases will be used for the descriptive analysis.

6.3.10. Improvement on Depression Subscale of HADS

- Improvement on HADS among subjects with a baseline subscale score indicative of depression who achieved a “normal” subscale score indicative of an absence of depression at Weeks 4, 8, 12, 24, and 48.
- Population: Subjects from the FAS with a baseline subscale score indicative of depression (ie, depression subscale score >7 for adults, depression subscale score >6 for adolescents).
- Statistical Method: MN up to week 24. Descriptive method for entire duration.
- Missing Data: Observed Case.

6.3.11. Improvement on Anxiety Subscale of HADS

- Improvement on HADS among subjects with a baseline subscale score indicative of anxiety who achieved a “normal” subscale score indicative of an absence of anxiety at Weeks 4, 8, 12, 24, and 48.
- Population: Subjects from the FAS with a baseline subscale score indicative of anxiety (ie, anxiety subscale score >7 for adults, anxiety subscale score >8 for adolescents).
- Statistical Method: MN up to week 24. Descriptive method for entire duration.
- Missing Data: Observed Case.

6.3.12. Change From Baseline in SF36v2 Acute

- Change from baseline in the physical and mental component scores, and 8 domain scores of the SF36v2 Acute at Weeks 4, 8, 12, 24, and 48.
- Population: FAS.
- Statistical Method: Descriptive statistics.
- Missing Data: Observed Case.

6.3.13. Change From Baseline in CGI-AA

- CGI-AA scored as 0=‘None (no hair loss)’, 1=‘Minimal hair loss’, 2-4=‘Moderate-very severe or complete hair loss’ at Weeks 4, 8, 12, 18, 24, 28, 34, 40, and 48.
- Improvement among participants with a baseline score 2-4 indicating moderate-very severe or complete hair loss, who achieved a score of 0=‘None (no hair loss)’ or 1=‘Minimal hair loss’ at Weeks 4, 8, 12, 18, 24, 28, 34, 40, and 48.
- Population: FAS.

- Statistical Method: Descriptive statistics.
- Missing Data: Observed Case.

6.3.14. Change From Baseline in Number of Fingernails Affected by AA

- Change from baseline in the number of fingernails affected by AA at Weeks 12, 24, 34, 40, and 48.
- Population: FAS: on the subset of subjects who have at least one affected fingernail at baseline.
- Statistical Method: Descriptive statistics.
- Missing Data: Observed Case.

6.3.15. Change From Baseline in IP-10

- Change from baseline in IP-10 at Weeks 4, 8, 12, and 24.
- Population: FAS.
- Statistical Method: Descriptive statistics.
- Missing Data: Observed Case.

6.3.16. Change From Baseline in T-cell, B-cell, and NK Cells

- Change from baseline in percent and absolute lymphocyte subsets (T-cell, B-cell, and natural killer [NK] cells) at Weeks 4, 12, 24, and 48.
- Population: FAS.
- Statistical Methods: Descriptive statistics for absolute or percent change from baseline. Counts and percent of patients in each category of CTCAE grade.
- Missing Data: Observed Case.

6.3.17. Change From Baseline in IgA, IgG, IgM

- Change from baseline in immunoglobulins (IgA, IgG, IgM) at Weeks 24 and 48.
- Population: FAS.
- Statistical Method: Descriptive statistics for change from baseline. Counts and percent of patients categories determined by clinical team.
- Missing Data: Observed Case.

